6.16.2.2. Analyses of Treatment-emergent ADA Effects on Efficacy

Efficacy analyses for the Blinded Treatment Period (Period 2) and Open-label Treatment Period (Period 3) will be conducted on all evaluable patients within the ITT Population.

Analyses will be performed to examine how patient TE-ADA effects sPGA of Genitalia (0,1) at week 12 with NRI by the TE-ADA status groups as described in Section 6.16.1.2. Note that the TE-ADA negative category will also be included in the NAb status and TE-ADA titer group analyses.

For sPGA of Genitalia (0,1) at Week 12, a logistic regression model with treatment group, TE-ADA status and the interaction of treatment group-by-TE-ADA status included as factors will be used to test the interaction of treatment group-by-TE-ADA status. The p-value associated with the interaction term will be used to assess if the treatment groups effect is consistent across TE-ADA status groups. When the interaction term is statistically significant, the association between responder status and treatment groups depends, in some manner, on the status. The interaction will be tested at the 10% significance level. Treatment group differences will be evaluated within each subgroup using Fisher's exact test regardless of whether the interaction is statistically significant.

6.16.2.3. Analyses of Treatment-emergent ADA on Specific Adverse Events

The analyses of ADA effects on safety will be conducted on all evaluable patients within the defined safety population for Period 2 and Open-Label Treatment Population for Period 3.

Adverse events of special interest of allergic reaction/hypersensitivity (anaphylaxis and non-anaphylaxis) and of injection-site reactions will be included in an assessment of AE to TE-ADA over time. See Section 6.15.3.1 for the definitions of the AESIs. Timing of an AE will be taken to be the reported AE start date.

For each TE-ADA status dichotomous variable (as defined in Table RHBQ.6.9), patients will be categorized according to whether they were (i) always in lesser-TE-ADA status post-baseline or (ii) at some point post-baseline, were in greater-TE-ADA status. For each AESI, within the time-varying TE-ADA status groups, a summary will be provided of the number of patients who had no event, events only while in lesser-TE-ADA status for group (i), or – for group (ii) – at least one event while in greater-TE-ADA status.

Additionally, summaries will be provided of the total number of AESI events (with unique start dates) by time-varying TE-ADA status groups at the event date. The summaries will aggregate time respectively in greater-TE-ADA status and in lesser-TE-ADA status, along with the event rates (rates per 100 patient-years) relative to those aggregate times.

By-patient listings will be provided of patients with TE-ADA who experience a treatment-emergent allergic reaction/hypersensitivity reaction or an injection site reaction.

6.17. Subgroup Analyses

6.17.1. Efficacy Subgroup Analyses

Subgroup analysis will be conducted for the primary endpoint at Week 12 using the ITT Population for the Blinded Treatment Period (Period 2).

- **The proportion of patients achieving an sPGA of Genitalia (0,1) (primary endpoint):** a logistic regression model with treatment, subgroup, and the interaction of treatment-by-subgroup as factors will be used. The treatment-by-subgroup interaction will be tested at the significance level of 0.10. Treatment group differences will be evaluated within each category of the subgroup using Fisher's exact test, regardless of whether the interaction is statistically significant. Missing data will be imputed using NRI, as described in Section 6.3.1. If any group within the subgroup is less than 10% of the total population, only descriptive statistics will be provided for that subgroup (that is, no inferential testing will be done).

The following subgroups will be analyzed:

- BSA category (<10%, ≥10%)
- Sex (male, female)
- Age category (<40 years, ≥40 years)
- Geographic Region (US [including Puerto Rico], non-US)

6.17.2. Safety Subgroup Analyses

Safety subgroup analysis for common TEAEs and AESI of allergy reaction/hypersensitivity and infections will be summarized by treatment group and overall, using the Safety Population for the Blinded Treatment Period (Period 2). The common TEAEs will be presented by MedDRA PT within SOC. The AESI of allergy reaction/hypersensitivity will be presented by anaphylaxis and non-anaphylaxis events, by PT within category. The AESI of infection will be presented by PT.

A logistic regression model with treatment group, subgroup, and the interaction of subgroup-by-treatment group as factors will be used. The subgroup-by-treatment group interaction will be tested at the significance level of 0.10. The response variable will be each AE. Treatment group differences will be evaluated within each category of the subgroup using Fisher's exact test, regardless of whether the interaction is statistically significant. If any group within the subgroup is less than 10% of the total population, only the descriptive statistics will be provided for that subgroup (that is, no inferential testing will be done).

The following subgroups will be analyzed:

- BSA category (<10%, ≥10%)
- Sex (male, female)

- Age category (<40 years, ≥40 years)
- Geographic Region (US, non-US)

6.18. Interim Analyses

An interim (primary) database lock and the unblinding (of Lilly personnel) will occur and the interim analysis will be performed at the time (that is, a cut-off date) the last patient completes Visit 7 (Week 12) or ETV. This interim database lock will include all data collected up to the cut-off date including follow-up data from patients that have begun Post-Treatment Follow-up Period (Period 4). Because the study will still be ongoing for the Post-Treatment Follow-up Period at the time of this database lock, the analysis will be referred to as an interim analysis. This interim analysis will include the final analysis for the Blinded Treatment Period (Period 2) of the study; therefore, there will be no alpha adjustment due to this interim analysis.

A final database lock will occur after the Post-Treatment Follow-up Period is completed.

6.19. Clinical Trial Registry Analyses

Additional analyses will be performed for the purpose of fulfilling the Clinical Trial Registry (CTR) requirements. Analyses provided for the CTR requirements include summary of AEs, provided as a dataset which will be converted to an XML file. Both SAEs and ‘Other’ AEs are summarized: by treatment group, by MedDRA preferred term.

- An AE is considered ‘Serious’ whether or not it is a treatment emergent adverse event (TEAE).
- An AE is considered in the ‘Other’ category if it is both a TEAE and is not serious. For each SAE and ‘Other’ AE, for each term and treatment group, the following are provided:
 - the number of participants at risk of an event
 - the number of participants who experienced each event term
 - the number of events experienced.
- Consistent with www.ClinicalTrials.gov requirements, ‘Other’ AEs that occur in fewer than 5% of patients/subjects in every treatment group may not be included if a 5% threshold is chosen (5% is the minimum threshold).
- AE reporting is consistent with other document disclosures such as the CSR.

6.20. Exploratory Analyses

Exploratory analyses other than those mentioned in [Table RHBQ.6.5](#) and [Section 6.20.1](#) may be added to future versions of this analysis plan, as deemed appropriate.

6.20.1. Psychometric Analyses of Diary Endpoints and sPGA of Genitalia

6.20.1.1. Psychometric Evaluation Overview

Psychometric evaluation is an iterative process beginning with qualitative assessment and also involving quantitative evaluation, wherein item and scale quality are examined to eliminate poorly performing or redundant items, to assess the scale structure and content validity, and to evaluate the measure's relationship to previously utilized and validated measures with regard to the constructs that the instrument is intended to measure. This section describes analyses that will be conducted to evaluate the psychometric properties of the GPSS, GPSIS, SFQ, and sPGA of Genitalia. No single test can be used to determine the psychometric qualities of an instrument; instead, a series of tests are proposed, each designed to evaluate a different aspect of the instrument's performance. Upon completion of the psychometric analyses, an overall summary regarding the psychometric properties of the instrument will be made, based on the analysis results. The following analyses will be conducted for each instrument where possible:

- Sample and item descriptive analyses, item level evaluation, and scaling, which will include descriptive item statistics, floor and ceiling effects.
- For measures with multiple items (for example, GPSS) the dimensionality of the measure will be explored using factor analyses.
- Assessment of the measurement properties of the instruments, including reliability, validity and responsiveness.
- Instrument descriptive analyses for the daily diary, including evaluation of the reliability and validity of the recall periods.

6.20.1.2. Statistical Analysis

6.20.1.2.1. General Considerations

- All statistical tests will use a two-sided significance level of 0.05, unless otherwise noted. Statistical tests involving multiple comparisons (e.g., analysis of covariance [ANCOVA] models with multiple groups) will include Scheffe post-hoc tests which adjust for multiple comparisons and reduce the possibility of Type I errors.
- Mplus software Version 7.3 (Muthén and Muthén 1998–2012) will be used to conduct exploratory and confirmatory factor analysis.
- SAS statistical software will be used for the remaining psychometric analyses. All SAS codes that are prepared for these analyses will be validated in line with the expectations of the Food and Drug Administration (FDA) and European Medicines Agency (EMA).
- The scoring of all measures used in the analyses (for example, DLQI, SF-36) will be provided by the developers of the instruments and documented elsewhere in the SAP.

- Most analyses outlined below will be conducted using the ITT population. Unless stated otherwise, the analyses involving the subscale of GPSIS, Sexual Activity Avoidance Subscale, will be restricted to patients who answered “Yes” or “No due to my genital psoriasis” in GPSIS Item #1.

6.20.1.2.2. Descriptive Statistics

Descriptive statistics (sample size, mean, SD, minimum, median, maximum, and % missing) will be calculated for the diary endpoints, including total score and item score and relevant subscale, and sPGA of Genitalia at baseline and Week 12.

The frequency distributions for item responses will be calculated for each item within the GPSS, each subscale within the GPSIS, and each item within the SFQ, as well as for the sPGA of Genitalia at baseline and Week 12.

6.20.1.2.3. Factor Analysis

Exploratory Factor Analysis (EFA) will be conducted using baseline GPSS data. Exploratory Factor Analysis will be used to uncover the underlying factor structure of the measures. Screen plots and corresponding eigenvalues will be examined to empirically inform the number of factors underlying the GPSS items. Factor loadings, standardized mean square residual (SRMR), and root mean square error of approximation (RMSEA) will be examined to evaluate model goodness-of-fit. It is recommended that the SRMR and RMSEA values be less than 0.8. Orthogonal and/or oblique rotation (Yates 1987) will be used in the analysis since the factors are expected to be correlated. An approximate simple structure will be the criterion for accepting a factor solution; oblique rotation will be conducted and correlations between factors will be reported, if necessary.

The GPSS includes multiple items and these analyses will evaluate the performance of each item in order to identify items that may be redundant or perform poorly. Items with low standardized loading <0.40 , or items with similar factor loadings across multiple domains indicate items that may be candidates for removal. Interpretability of factors and clinical judgment will also be considered in the selection of the final model.

Confirmatory factor analysis (CFA) will be conducted using Week 1 data to evaluate the conceptual framework for the GPSS. It is hypothesized that the GPSS will yield a one factor solution similar to other symptom measures for plaque psoriasis (Revicki et al. 2014). Confirmatory factor analysis will be conducted to model factor loadings based on the final conceptual model derived in the EFA analyses.

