5.3. Determination of Sample Size

The total sample size for the study will be approximately 146 patients randomized at 1:1 ratio in the Blinded Treatment Period to ixekizumab Q2W and placebo (73 patients per treatment group).

No prior static Physician's Global Assessment (sPGA) of Genitalia (primary outcome measure) data was available at the time of planning this study to guide sample size and power calculations because no biologic drug has been evaluated in a well-controlled clinical trial to date in patients with genital psoriasis. Therefore, based on the relevance and impact of sexual impairment in genital psoriasis, data from the assessment of the Dermatology Life Quality Index (DLQI) Item 9 (How much has your skin caused any sexual difficulties?) outcomes in the ixekizumab Phase 2 and Phase 3 studies were used to calculate the sample size. Sample size was calculated assuming sexual impairment rates of 2% and 20% in the ixekizumab Q2W and placebo treatment groups, respectively. With these assumed rates, a sample size of 146 (73 per treatment group) is likely to achieve 94% power, based on a 2-sided Fisher's exact test at 0.05 level of significance.

6. A Priori Statistical Methods

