GPSS	
The Genital Psoriasis Symptoms Scale (GPSS) is a patient-administered assessment of 8 symptoms: itch, pain, discomfort, stinging, burning, redness, scaling, and cracking. Respondents are asked to answer the questions based on their psoriasis symptoms in the respective genital areas.
 
The overall severity for each individual symptom from patient's genital psoriasis is indicated by selecting the number from an NRS of 0 to 10 that best describes the worst level of each symptom in the genital area in the past 24 hours, where 0 (= no severity) and 10 (worst imaginable severity).
 
The symptom severity scores, ranging from 0 to 10, are the values of the selected numbers indicated by the patient on the instrument's horizontal scale. Each of the 8 individual items will receive a score of 0 to 10 and will be reported as item scores for itch, pain, discomfort, stinging, burning, redness, scaling, and cracking. In addition, a total score ranging from 0 (no genital psoriasis symptoms) to 80 (worst imaginable genital psoriasis symptoms) will be reported.
	GPSS total score	
The GPSS total score will be calculated by summing the individual item scores as follows: GPSS = itch NRS + pain NRS + discomfort NRS + stinging NRS + burning NRS + redness NRS + scaling NRS + cracking NRS
 
The GPSS total score at Week 12 (Visit 7) is the average of at least 4 non-missing scores of the last 7 consecutive days. The 7-day window ends on the date of Visit 7 when the data is collected on site, and on or after the date of previous visit.
 
The GPSS total score at Week 2 (Visit 4), Week 4 (Visit 5), and Week 8 (Visit 6), is the average of at least 4 non-missing scores of the last 7 consecutive days before the date of current visit, and on or after the date of previous visit.
 
The GPSS total score at Week 1 (Visit 3), the 7-day window is before the date of Visit 3, and on or after the date of the first injection.
 
Note 1: For derivations of post-baseline visit scores, when there are less than 4 non-missing scores in the 7-day window, the window will be extended one day at a time, up to 10 days, until 4 non-missing scores are found, but the window will not be extended beyond the date of previous visit. If at least 4 non-missing scores are still not found, the visit score will be designated as missing.
 
Note 2: When 7-day duration is not present between visits, the visit score will be the average of at least 4
	If any item score is missing, the GPSS total score will be missing.

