6.20.1.2.5. Psychometric Analyses

Following the examination of the distributional characteristics of measures, the following psychometric properties of the instruments will be evaluated: internal consistency (GPSS only), test-retest reliability, convergent validity, known-groups validity and sensitivity to change (responsiveness) using anchor- and distribution-based methods.

6.20.1.2.5.1. Internal Consistency

Internal consistency reliability addresses the extent to which individual items in the instrument measure a common underlying concept by examining the item-item or item-total, correlations for the GPSS using Cronbach’s coefficient alpha (Cronbach 1951).

The values are presented descriptively on an interval level scale from 0 to 1.0, with higher scores indicating a more reliable (homogeneous) instrument. Cronbach’s alpha coefficients between 0.7 and 0.9 will indicate good internal consistency, values between 0.4 and <0.7 will indicate moderate internal consistency, and values <0.4 will indicate low internal consistency reliability (Nunnally and Bernstein 1994, Cronbach 1951). Cronbach’s alphas greater than 0.70 are generally considered acceptable for group comparisons (Hays and Revicki 2005). Internal consistency reliability will be assessed for the GPSS at the day prior to the first study drug injection and again at the day prior to the Week 12 injection based on item-level data. Cronbach’s alpha for the GPSS total score and a summary of Cronbach’s alpha levels with each constituent item deleted will also be reported.

Pearson and Spearman correlations will be used to calculate inter-item correlations for GPSS items. These correlations examine the extent to which items within the measure related to each other. These correlations will be used to confirm that the measures are performing in this sample as expected. Items will be flagged as being potentially redundant/overlapping when the item-item correlation is greater than 0.80.

6.20.1.2.5.2. Test-Retest Reliability

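### The recommended SRMR and RMSEA limit of 0.8 in the GPSS factor analysis is too loose to flag plausible misfit

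*SAP*

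**What the plan says.** SAP 6.20.1.2.3 plans an exploratory factor analysis (EFA) of the GPSS items at baseline, then a confirmatory one (CFA) at Week 1. The exploratory paragraph lists loadings, SRMR and RMSEA as evidence on goodness of fit and adds: "It is recommended that the SRMR and RMSEA values be less than 0.8". No other number in the section limits overall fit.

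The same section names further evidence:
- Number of factors: "Screen plots and corresponding eigenvalues will be examined to empirically inform the number of factors underlying the GPSS items".
- Acceptance: "An approximate simple structure will be the criterion for accepting a factor solution".
- Items: a standardized loading below 0.40, or similar loadings on several domains, makes an item a candidate for removal.
- Final model: interpretability and clinical judgment also count.

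On the expected result the section says "It is hypothesized that the GPSS will yield a one factor solution". It gives no fit limit for the confirmatory analysis.

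**The concern.** SRMR and RMSEA are there to show when a fitted model reproduces the observed correlations badly. A limit does that job only if badly wrong models exceed it. SRMR is on the scale of a residual correlation, so a limit of 0.8 tolerates residuals about as large as the correlations themselves.

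At stake is what a reader of the psychometric report is told. A poorly fitting model would be described as within the plan's recommended limit, and that statement would carry no information. The plan expects one factor, so an uninformative fit check leans towards confirming the expectation.

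**Working it through.** **Inputs.**
- Limit: 0.8 on both indices (SAP 6.20.1.2.3). It is a chosen cut-off with nothing behind it to reproduce, so it is tested instead.
- Items: p = 8. SAP 6.10, Table RHBQ.6.4, describes a "patient-administered assessment of 8 symptoms: itch, pain, discomfort, stinging, burning, redness, scaling, and cracking". That gives 8×7/2 = 28 correlations, or 36 elements with the diagonal. Degrees of freedom are 28 for a no-factor model and 36 − 16 = 20 for a one-factor model.
- Sample size: "The total sample size for the study will be approximately 146 patients randomized at 1:1 ratio" (SAP 5.3). On population, SAP 6.20.1.2.1 says "Most analyses outlined below will be conducted using the ITT population".
- Inter-item correlation: no expected value is given. Equal correlations r are assumed and a range is shown.

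**Step 1: a model with no factor.** It predicts zero for every correlation, so
- SRMR = r × √(28/36) = 0.882 r
- RMSEA = √(F/28), with F = −[7 ln(1 − r) + ln(1 + 7r)]

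At r = 0.7, SRMR = 0.882 × 0.7 = 0.617. F = −[7 × (−1.204) + 1.775] = 6.653, so RMSEA = √(6.653/28) = 0.487.

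| r | SRMR | RMSEA | Both below 0.8? |
|---|---|---|---|
| 0.3 | 0.265 | 0.221 | yes |
| 0.5 | 0.441 | 0.346 | yes |
| 0.7 | 0.617 | 0.487 | yes |
| 0.8 | 0.706 | 0.579 | yes |
| 0.9 | 0.794 | 0.710 | yes |
| 0.95 | 0.838 | 0.822 | no |

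The SRMR limit is reached at r = 0.8/0.882 = 0.907 and the RMSEA limit at r = 0.942, so the model passes both up to about 0.91. If SRMR is averaged over the 28 off-diagonal terms only, it equals r and the limit is reached at 0.80.

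**Step 2: sampling at N = 146.** In 2,000 simulated normal samples per value of r, the no-factor model met both limits in 100% of samples for the values of r tried from 0.3 to 0.8, in 99.95% at 0.85 and in 73% at 0.9.

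**Step 3: the SAP's own benchmarks.** SAP 6.20.1.2.5.1 calls Cronbach's alpha of 0.7 to 0.9 good. For eight equally correlated items, r = alpha/(8 − 7 alpha): 0.7/3.1 = 0.226 and 0.9/1.7 = 0.529. Over that range the no-factor model has SRMR 0.199 to 0.467 and RMSEA 0.174 to 0.365. The same section says "Items will be flagged as being potentially redundant/overlapping when the item-item correlation is greater than 0.80". With SRMR over all 36 elements, the 0.8 limit starts to bite only at r of about 0.907, where alpha is 8 × 0.907/(1 + 7 × 0.907) = 0.987 and every pair would already be flagged.

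**Step 4: a wrong one-factor model.** Take two blocks of four items, correlated 0.8 within and 0.2 between. A one-factor maximum-likelihood fit gives SRMR 0.30 and RMSEA 0.41. Across other two-factor truths (loadings 0.6 to 0.95, factor correlation 0 to 0.5), SRMR runs from 0.08 to 0.37 and RMSEA from 0.12 to 0.53. All meet 0.8.

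**Step 5: the same checks at 0.08.** The no-factor model passes only up to r = 0.08/0.882 = 0.091 on SRMR and 0.092 on RMSEA. In the simulation it passed in 0% of samples for every r tried from 0.3 to 0.9. The two-block example fails on both indices. Every other one-factor fit in Step 4 fails on RMSEA. The mildest (loadings 0.6, factor correlation 0.5) has SRMR 0.079 and fails on RMSEA alone, at 0.12.

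**The case against.** The strongest reply is that the limit carries little weight in the plan. It is a recommendation, not an accept-or-reject rule, and SAP 6.20.1.1 says that no single test settles the quality of an instrument. The two-block example would be caught by the eigenvalue step: its eigenvalues are 1 + 3(0.8) ± 4(0.2), that is 4.2 and 2.6, then six of 0.2, which plainly shows two factors. The plan does not force one factor on the data, because the confirmatory model follows from the exploratory result. Nor does any step put forward a model with no factor. All of this stands, and it bounds the point.

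It also rules out four stronger readings that a reader might infer:
- **That the test of GPSS structure cannot fail.** Eigenvalues, loadings, simple structure and judgment can each reject a structure.
- **That a no-factor model always passes.** It fails above r of about 0.91, or 0.80 with off-diagonal SRMR.
- **That the GPSS total score or item removal depends on this limit.** Protocol 8.1.2.2.1 and SAP Table RHBQ.6.4 fix the total as a sum of eight items, and item removal rests on loadings.
- **That trial conclusions are exposed.** The psychometric objective is exploratory (SAP 4.3), and the GPSS total is an other secondary endpoint (SAP 4.2) outside the testing sequence in SAP 6.4.

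The reply does not rescue the figure. Other criteria can do their work without making a limit that passes nearly everything informative.

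**Conclusion.** Wrong as written, minor. The SRMR/RMSEA limit does not separate acceptable from badly wrong models over any plausible range of correlations for eight items. The consequence is confined to how fit is described in the exploratory psychometric analysis.

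The no-factor figures assume equal inter-item correlations, and the simulation also assumes normal data and all 146 patients. The population limits do not depend on sample size. The wrong-model figures assume two blocks of four items.

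That 0.08 was meant is an inference. A slipped decimal is plausible, since the same paragraph has another apparent misprint (Screen for scree), but neither document gives 0.08.

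**What to change.** In SAP 6.20.1.2.3, replace 0.8 with a limit that discriminates. If a decimal slipped, that is 0.08 for both indices. If another value was intended, state it and give the reason. Say whether the same limit applies to the Week 1 confirmatory analysis, which has none at present.

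The cost is one figure and one sentence. Data collection, trial conduct and the alpha allocation are unchanged. The only consequence is that a poorly fitting model may now have to be reported as such.
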